13.4.2 Early Stopping for Safety in the Post-Transplant Setting

Because many patients enrolled in this protocol will be candidates for a subsequent allo-HSCT, and there have been recent reports of increased toxicity among patients who undergo allo-HSCT following treatment with PD-1 inhibitors, all patients who go onto allo-HSCT following the completion of the clinical protocol will undergo continuous monitoring. The clinical failures of acute grade 3-4 graft versus host disease and post-transplant non-relapse mortality will be monitored continuously for the first 100 post-transplant days. If it becomes evident that the proportion of acute grade 3-4 graft versus host disease is greater than 25% or the proportion of non-relapse mortality is greater than 20% then the study would be held for a safety consultation.

Acute Grade 3-4 GVHD

The acute GVHD grade 3-4 stopping rule will hold enrollment if the posterior probability of failure being larger than 0.25 is 70% or higher. The prior for this monitoring rule is beta(1,3). This means that our prior guess at the proportion of failures is 25%, and there is 90% probability that this proportion is between 1.7% and 63.2%. The following table shows the resulting rules.

Safety review triggered if number of patients with grade 3-4 GVHD is:	2	3	4	5	6	7	8	9	10	11
Number of patients is between:	2-4	5-8	9-11	12-15	16-18	19-22	23-26	27-30	31-33	34-36

For example, the rule will call for a safety review if 3 out of the first 5 patients experience acute grade 3-4 GVHD. The table below shows the percent of times the stopping rule will halt the study for a safety review and the average sample size under different hypothetical risks of grade 3-4 acute GVHD.

Operating Characteristics of stopping rule for GVHD, based on 5000 simulations:

True acute or chronic GVHD grade 3-4 rate	Probability of stopping for excess GVHD grade 3-4	Average Sample Size
10%	8.0%	31.7
15%	20.7%	28.4
20%	37.1%	24.6
25%	58.5%	19.4
30%	77.3%	14.9
35%	89.2%	11.3
40%	95.9%	8.4

Non-Relapse Mortality

The non-relapse mortality safety stopping rule will hold enrollment if the posterior probability of failure being larger than 0.20 is 70% or higher. The prior for this monitoring rule is beta(1,4). This means that our prior guess at the proportion of failures is 20%, and there is 90% probability that this proportion is between 0.60% and 60.2%. The following table shows the resulting rules.

Safety review triggered if number of patients with non-relapse mortality is:	2	3	4	5	6	7	8	9
Number of patients is between:	2-5	6-9	10-14	15-18	19-23	24-27	28-32	34-36

For example, the rule will call for a safety review if 4 out of the first 10 patients die without relapse. The table below shows the percent of times the stopping rule will halt the study for a safety review and the average sample size under different hypothetical risks of non-relapse mortality.

Operating Characteristics of stopping rule for non-relapse mortality, based on 5000 simulations:

True Non-Relapse Mortality Rate	Probability of stopping for too much non-relapse mortality	Average Sample Size
10%	13.0%	30.5
15%	31.0%	26.3
20%	53.7%	21.0
25%	74.3%	16.1
30%	89.6%	11.6
35%	96.2%	8.9

13.4.3 Statistical Analysis Plan

The primary objective of this study is to evaluate the safety and tolerability of blinatumomab given in combination with nivolumab, or in combination with both nivolumab and ipilimumab in subjects with poor-risk, relapsed or refractory CD19⁺ Pre-B cell ALL or CD19⁺ biphenotypic

leukemia. All adverse events and toxicities will be tabulated and reported by type and grade for all dose levels of all treatment combinations and the proportions reported with exact 95% binomial confidence intervals. Any patient who receives at least one dose of any treatment will be included in toxicity reporting, regardless of eligibility or study drop out.

13.5 Sample Size/Accrual Rate

In the dose escalation phase of this study, the sample size is determined by the number of DLTs observed. The minimum sample size for this first part of the study will be 6 patients at DL1 and DL-1 (if necessary), and a maximum sample size of 12 patients. During the dose escalation phase of the combination arm, the minimum number of patients treated will be 3 and maximum will be 6 at each dose level. If the combination is deemed safe and the expansion cohort is enrolled, the sample size will be either 9 or 12 at that dose level. The maximum total sample for the entire study will be 36 patients.

The anticipated complete response (CR) rate in this patient population is approximately 40%. With a minimum sample size of 12 subjects in the combination arm, the probabilities of observing at least 5 responses out of 12 patients (41.7% CR rate) would be 0.42, 0.56, and 0.70 if the true CR rate is 35%, 40%, and 45%, respectively. If the true CR rate is less than 15%, the chance of observing 5 responses out of 12 would be 0.024 or less. This sample size also allows for estimation of the CR rate with precision (half the width of the 95% exact binomial confidence interval) being no wider than 25.5%.

PLANNED ENROLLMENT REPORT

Racial Categories	Ethnic Categories				Total
	Not Hispanic or Latino		Hispanic or Latino		
	Female	Male	Female	Male	
American Indian/ Alaska Native	0	0	0	0	0
Asian	1	0	0	0	1
Native Hawaiian or Other Pacific Islander	0	0	0	0	0
Black or African American	1	2	0	0	3
White	7	13	3	3	26
More Than One Race	0	0	0	0	0
Total	9	15	3	3	30

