When the safety of blinatumomab in combination with nivolumab has been established as above, the trial will proceed to either DL B1 or DL B-1, and a standard 3+3 dose escalation design for blinatumomab and nivolumab with ipilimumab will be used to ascertain the safety of this combination. Two dose levels (DL B-1, DL B1) may be used to evaluate this combination. Depending on the results from the combination of blinatumomab and nivolumab as outlined above, patients will first be enrolled at either DL B1 or DL B-1. If ≤ 1 of 3 patients experiences a DLT at DL B1, an additional 3 patients will be enrolled at DL B1. If ≤ 1 of 6 patients experience a DLT, then this will be defined as the MTD. If ≥ 2 or more of 3 or 6 patients experience a DLT at DL B1, then dose de-escalation may be implemented BUT ONLY after thorough evaluation of toxicities, discussion with CTEP, investigators and CTEP agreement and the next three patients may be enrolled at DL B-1. If the triplet combination starts at DL B-1 based on the results from the combination of blinatumomab and nivolumab alone, then three patients will be enrolled at DL B-1. If ≤ 1 of 3 patients experiences a DLT at DL B-1, an additional 3 patients will be enrolled at DL B-1. If no more than 1 of 6 patients experience a DLT at DL B-1, then this dose level will be defined as MTD. If 2 or more of 3 or 6 patients experience a DLT at DL B-1, then dose escalation will be halted and the combination of blinatumomab, nivolumab and ipilimumab will not be further pursued in this patient population unless additional data become available supporting different doses or schedules of nivolumab and ipilimumab administration. This will require review of all toxicity, discussion with CTEP and official study amendment. The MTD of blinatumomab in combination with nivolumab and ipilimumab is defined as the highest dose at which no more than 1 out of 6 patients experience a DLT. When the MTD of blinatumomab in combination with nivolumab and ipilimumab is determined, an additional 6 patients will be enrolled in an expansion cohort to further characterize safety, tolerability and any preliminary signs of biological or clinical activity. An expansion cohort of an additional 6 patients at the MTD of blinatumomab and nivolumab without ipilimumab will be also pursued to further characterize safety, tolerability and any preliminary signs of biological or clinical activity for this combination. The expansion cohort at the MTD of blinatumomab and nivolumab will be open for enrollment while dose-escalation continues for blinatumomab, nivolumab and ipilimumab. Enrollment priority: Patients will be enrolled in dose-escalation cohort for blinatumomab, nivolumab and ipilimumab first. However, if no slots are available, patients will be allowed to enroll in dose expansion cohort for blinatumomab and nivolumab. Once the MTD for blinatumomab, nivolumab and ipilimumab is defined, the enrollment in dose expansion cohorts

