13.3.2 Secondary Objectives

- 13.3.2.1 The frequency distribution of responses, including CR, CRi or progressive disease (PD) by treatment arm and dose level for all patients on study will be determined and reported with exact 95% confidence intervals.

- 13.3.2.2 For patients who have a clinical response, the frequency of MRD+ vs. MRD-responses will be reported by treatment arm and dose level for all patients on study.
- 13.3.2.3 For patients who have a clinical response, duration of response (DOR) will be analyzed as a time-to-event outcome with the duration being measured as the time from measured response to progressive disease, death, or study end.
- 13.3.2.4 Overall survival will be measured from the first day of treatment on the study until death or last known follow up.

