13.7 Analysis of Secondary Endpoints

The secondary objectives of this study include describing preliminary antileukemia activity of blinatumomab and nivolumab, and blinatumomab plus both nivolumab and ipilimumab, including the effects on MRD, and assessing preliminary antileukemia activity in an expansion cohort of patients with poor-risk, relapsed or refractory CD19⁺ Pre-B cell ALL. The frequency distribution of responses, including CR, CRi or progressive disease (PD) will be reported by treatment arm and dose level for all patients on study and reported with exact 95% confidence intervals. For patients who have a clinical response, duration of response (DOR) will be analyzed as a time-to-event outcome using the Kaplan Meier method with the duration being measured as the time from measured response to progressive disease, death, or study end. A sensitivity analysis may be performed to evaluate DOR while excluding patients who go on to have an allo-HSCT. Overall survival will be measured using the Kaplan Meier method as the time from the first day of treatment on the study until death or last known follow up.

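### The 25.5% precision stated for the CR rate is not a 95% figure at n = 12: the exact 95% half-width reaches 28.9%

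*Combined protocol and SAP*

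**What the plan says.** Section 13.5 bases its CR calculations on 12 patients: "With a minimum sample size of 12 subjects in the combination arm". For that size it gives probabilities of at least 5 responses of 0.42, 0.56 and 0.70 at true CR rates of 35%, 40% and 45%, and of 0.024 or less if the true rate is below 15%. It then adds: "This sample size also allows for estimation of the CR rate with precision", defined as "half the width of the 95% exact binomial confidence interval) being no wider than 25.5" per cent. The type of exact interval is not named.

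The 95% level agrees with the reporting plan. Section 13.3.2 says the response distribution "will be determined and reported with exact 95% confidence intervals", and Section 13.7 plans the same: "by treatment arm and dose level for all patients on study and reported with exact 95% confidence intervals". Neither section mentions a 90% interval.

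On cohort size, the preceding paragraph of Section 13.5 says that once the expansion cohort is enrolled "the sample size will be either 9 or 12 at that dose level".

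**The concern.** A half-width of 25.5% looks too small for a 95% exact interval on 12 patients near a rate of one half. The bound is worded as a ceiling, so a single possible count above it makes the statement false. With an anticipated CR rate of about 40%, the counts most likely to occur are the ones with the widest intervals. The intervals reported under Sections 13.3.2 and 13.7 would then probably be wider than the plan said they could be. What is at stake is the accuracy of the precision claim, not the design.

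**Working it through.** **Inputs.** From Section 13.5: n = 12; two-sided 95% exact binomial interval; stated maximum half-width 25.5%; anticipated CR rate about 40%. Assumption: exact means Clopper-Pearson. Other exact constructions are tried in step 4.

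**1. Is n = 12 the size the authors used?** P(X ≥ 5 | n = 12, p) from the binomial distribution:

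| True CR rate | Stated | Recomputed |
|---|---|---|
| 35% | 0.42 | 0.417 |
| 40% | 0.56 | 0.562 |
| 45% | 0.70 | 0.696 |
| 15% | 0.024 | 0.0239 |

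These agree, so the paragraph's other figures are right and n = 12 is confirmed.

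**2. Half-widths at n = 12.** For x responses, with α = 0.05 for the 95% interval and α = 0.10 for the 90% interval:

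- lower limit L = Beta quantile(α/2; x, n − x + 1), with L = 0 at x = 0
- upper limit U = Beta quantile(1 − α/2; x + 1, n − x), with U = 1 at x = n
- half-width = (U − L)/2

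The results are symmetric about x = 6:

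| x | 95% interval | 95% half-width | 90% half-width |
|---|---|---|---|
| 0 | 0% to 26.5% | 13.23% | 11.05% |
| 1 | 0.2% to 38.5% | 19.13% | 16.72% |
| 2 | 2.1% to 48.4% | 23.16% | 20.38% |
| 3 | 5.5% to 57.2% | 25.85% | 22.77% |
| 4 | 9.9% to 65.1% | 27.59% | 24.31% |
| 5 | 15.2% to 72.3% | 28.58% | 25.19% |
| 6 | 21.1% to 78.9% | 28.91% | 25.47% |

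The 95% maximum is 28.91%, which is 28.91 − 25.5 = 3.4 percentage points above the stated ceiling. Only 0 to 2 and 10 to 12 responses meet it. The 90% maximum is 25.47%, which rounds to 25.5%.

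**3. How often the bound would fail.** Under Clopper-Pearson it fails when 3 ≤ X ≤ 9. At true CR rates of 35%, 40% and 45% the probability of that is 0.85, 0.91 and 0.95.

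**4. Other exact 95% constructions, n = 12.**

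| Method | Maximum half-width | Excess over 25.5% |
|---|---|---|
| Sterne | 26.25% | 0.75 points |
| Blyth-Still-Casella | 26.45% | 0.95 points |
| Blaker | 26.57% | 1.07 points |
| Clopper-Pearson | 28.91% | 3.41 points |

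Wilson and Agresti-Coull do fall below 25.5% (both 24.62%), but they are approximate intervals, and the plan specifies an exact one.

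**5. Other sample sizes, 95% Clopper-Pearson maximum.** n = 9: 32.55%; n = 15: 26.07%; n = 16: 25.35%. A 25.5% ceiling at 95% would first be met at 16 patients.

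**6. The 9-or-12 statement.**

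- *Section 13.5, cohort range:* 3 to 6 patients per combination dose level, plus 6 in expansion, gives 9 or 12.
- *Section 13.5, CR paragraph:* 12 is the minimum.
- *Section 5.2.1:* if at most 1 of the first 3 patients "experiences a DLT at DL B1, an additional 3 patients will be enrolled at DL B1", and at the MTD "an additional 6 patients will be enrolled in an expansion cohort to further characterize safety". That gives 3 + 3 + 6 = 12. Section 13.4 has the same path.
- *Section 5.4, decision table:* no DLT in 3 patients leads to the next dose level, and the footnote requires six patients regardless of toxicity only at levels A1 and A-1. The last row, however, requires at least 6 patients at the recommended phase 2 dose.

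So 9 has some support in Sections 13.5 and 5.4, but it conflicts with the stated minimum of 12, with the path in Sections 5.2.1 and 13.4, and with the last row of the Section 5.4 table.

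**The case against.** The strongest reply is that nothing depends on this number. The 12 comes from 3 + 3 + 6, not from a precision target. CR is a secondary, descriptive endpoint, and the reported exact 95% intervals will be computed from the data whether or not this sentence is edited. All of that stands, and it limits the weight of the point.

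A second reply is that the size of the error depends on an assumed method. That is also right: the 3.4-point gap, the range of 3 to 9 responses and the failure probabilities in step 3 belong to Clopper-Pearson. Blaker exceeds 25.5% only at 4 to 8 responses and Sterne only at 5 to 7, so at a true rate of 40% the bound fails with probability 0.76 and 0.50, instead of 0.91. The direction does not change: no exact 95% method tried keeps within 25.5%.

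Third, the documents never mention a 90% interval, so the numerical match suggests the cause but does not prove it. Finally, the 9-or-12 conflict concerns cohort size, is separate from the precision error, and should be resolved separately.

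**Conclusion.** The precision statement is wrong as written. At n = 12 the ceiling on the 95% exact half-width is 28.91% under Clopper-Pearson, 3.4 points above the stated 25.5%, and 0.75 to 1.07 points above it under the other exact methods tried. The finding that the bound is broken holds for each of these methods; the 3.4-point size rests on reading exact as Clopper-Pearson. That a 90% figure was labelled as 95% is probable but not documented. The neighbouring response probabilities are correct. The error should be corrected, but it affects neither enrolment, nor any decision rule, nor the planned analysis.

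**What to change.** In Section 13.5, name the Clopper-Pearson method, keep the 95% level and replace 25.5% with about 28.9%. It would help to add that an observed 5/12 gives 15.2% to 72.3%, a half-width of 28.6%. Relabelling the interval as 90% would make the number true but would no longer match the 95% intervals planned in Sections 13.3.2 and 13.7. The cost is one sentence and a less favourable stated precision, with no change to enrolment or analysis.

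As a separate edit, reconcile the 9-or-12 wording with the minimum of 12 in the same section, the enrolment path in Sections 5.2.1 and 13.4, and the decision table in Section 5.4. If 9 patients remain possible, state the 95% ceiling for that size too, 32.55%.

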13.6 Stratification Factors

Not Applicable

13.7 Analysis of Secondary Endpoints

The secondary objectives of this study include describing preliminary antileukemia activity of blinatumomab and nivolumab, and blinatumomab plus both nivolumab and ipilimumab, including the effects on MRD, and assessing preliminary antileukemia activity in an expansion cohort of patients with poor-risk, relapsed or refractory CD19⁺ Pre-B cell ALL. The frequency distribution of responses, including CR, CRi or progressive disease (PD) will be reported by treatment arm and dose level for all patients on study and reported with exact 95% confidence intervals. For patients who have a clinical response, duration of response (DOR) will be analyzed as a time-to-event outcome using the Kaplan Meier method with the duration being measured as the time from measured response to progressive disease, death, or study end. A sensitivity analysis may be performed to evaluate DOR while excluding patients who go on to have an allo-HSCT. Overall survival will be measured using the Kaplan Meier method as the time from the first day of treatment on the study until death or last known follow up.

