5.3 Study Drugs

5.3.1 Blinatumomab

Blinatumomab will be administered as a continuous IV infusion over four weeks followed by a two-week treatment-free interval. It is recommended that patients are hospitalized at least during the first 14 days of the first cycle and the first two days of the subsequent cycles. The hospitalization time depends on the investigator's judgment, as well as safety and tolerability of blinatumomab.

Cycle 1: The planned initial dose of blinatumomab is 9 µg/day administered via continuous intravenous infusion on days 1-7 of the first 42-day cycle. If patients tolerate the initial infusion without significant adverse events, then the dose of blinatumomab will be escalated to 28 µg/day administered via continuous intravenous infusion on days 8-28 of cycle 1. There will be a minimum blinatumomab treatment-free interval of 14 days following the completion of blinatumomab infusion prior to the initiation of the next cycle. Patients will be eligible for up to five cycles of blinatumomab if they achieve complete remission (CR) or CR with incomplete hematologic recovery (CRh) following 1-2 cycles of treatment. Given that this is a group of patient with a very high risk ALL, patients will be eligible to proceed to allogenic HSCT at the treating physician's discretion at any time after a response is documented. For patients receiving **cycles 2-5**, the planned dose of blinatumomab is 28 µg/day to be administered via continuous infusion on days 1-28 of each 42-day cycle.

Blinatumomab should be infused at a constant flow rate using an infusion pump. The pump should be programmable, lockable, non-elastomeric, and have an alarm. Blinatumomab infusion bags should be infused over 24 or 48 hours according to the instructions on the pharmacy label on the bags (Section 8.1.1). The solution should be administered using IV tubing that contains a sterile, non-pyrogenic, low protein-binding, 0.2 micron in-line filter. The IV line should never be flushed, especially when changing bags or at the completion of infusion, due to the risk of excess dosage. Blinatumomab should be infused through a dedicated lumen. Nivolumab +/- ipilimumab will be infused through a separate line from blinatumomab to allow continuous blinatumomab infusion when nivolumab +/- ipilimumab are administered.

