5.7 Duration of Follow Up

Patients will be followed for overall survival and relapse every 3 months for 2 years after removal from study treatment or until death, whichever occurs first. Patients removed from study treatment for unacceptable adverse event(s) will be followed until resolution or stabilization of the adverse event. Assessments for toxicity/adverse events are to continue for 100 days after the last dose of nivolumab/ipilimumab. Because many patients enrolled in this protocol will be candidates for a subsequent allo-HSCT, and there have been recent reports of increased toxicity among patients who undergo allo-HSCT following treatment with PD-1 inhibitors, all patients who go onto allo-HSCT following the completion of treatment on the study will undergo continuous monitoring. The clinical failures of acute grade 3-4 graft versus host disease and post-transplant non-relapse mortality will be monitored continuously for the first 100 post-transplant days. We will also collect data on development of additional cancers, subsequent therapy for their cancer, and survival. Medical records including laboratory, pathology, operative, and radiology reports will be obtained at the discretion of the Protocol Chair.

All reasons for discontinuation of therapy should be documented clearly in the medical record. If a subject discontinues or withdraws from the study, every attempt will be made to get a bone marrow biopsy and study bloods if the subject is able and willing to do so.

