5.8 Criteria for Removal from Study

Patients will be removed from study treatment when any one of the applicable criteria listed in Section 5.6. is met. For this protocol, all patients, including those who discontinue protocol therapy early, will be followed for 2 years from the end of study treatment for relapse and for survival (even if non-protocol therapy is initiated). Patient will be removed from study if any one of the following criteria is met: completion of follow up period, patient withdraws consent from study, death, or patients is lost for follow up. The reason for study removal and the date the patient was removed must be documented in the Case Report Form.

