11.1.2 Disease Parameters

Complete Remission (CR)

- 1 No circulating blasts or extramedullary disease
 - No lymphadenopathy, splenomegaly, skin/gum infiltration/testicular mass/CNS involvement
- 2 Trilineage hematopoiesis (TLH) and <5% blasts
- 3 Absolute neutrophil count (ANC) >1,000/ μ L
- 4 Platelets >100,000/ μ L

CR with incomplete blood count recovery (CRi)

- Meets all criteria for CR except platelets and/or ANC

Refractory Disease

- Failure to achieve CR after 1-2 cycles of treatment

Progressive Disease (PD)

- Increase of at least 25% in the absolute number of circulating or bone marrow blasts or development of extramedullary disease

Relapsed Disease

- Reappearance of blasts in the blood or bone marrow (>5%) or in any extramedullary site after a CR

Minimal Residual Disease (MRD)

- MRD in ALL refers to the presence of leukemic cells below the threshold of detection by conventional morphologic methods. Patients who achieved a CR by morphologic assessment alone can potentially harbor a large number of leukemic cells in the bone marrow.

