11.1.5 Duration of Response

Duration of overall response: The duration of overall response is measured from the time criteria are met for CR or CRi (whichever is first recorded) until the first date that relapsed disease is objectively documented.

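### Duration of response is defined differently in 11.1.5 and in 13.3.2.3/13.7, with events and censoring not labelled; the optional transplant sensitivity analysis also selects responders by a later event

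*Combined protocol and SAP*

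**What the plan says.** **Definition of DOR.**
- Section 11.1.5 starts the clock at CR or CRi, whichever is recorded first, and runs it "until the first date that relapsed disease is objectively documented". Death is not mentioned.
- Section 13.3.2.3 measures DOR as "the time from measured response to progressive disease, death, or study end". Section 13.7 uses the same list and names the Kaplan-Meier method.
- Section 11.1.2 defines relapse as "Reappearance of blasts in the blood or bone marrow (>5%) or in any extramedullary site after a CR", and progressive disease as "Increase of at least 25% in the absolute number of circulating or bone marrow blasts or development of extramedullary disease".

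**Transplant.**
- Section 13.7 adds: "A sensitivity analysis may be performed to evaluate DOR while excluding patients who go on to have an allo-HSCT".
- Section 5.3.1 lets responders go to allogeneic transplant at the treating physician's "discretion at any time after a response is documented".
- Section 5.7 expects that "many patients enrolled in this protocol will be candidates for a subsequent allo-HSCT".
- Section 5.8 continues follow-up for relapse and survival for 2 years after study treatment, including after other therapy has begun.

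**The concern.** A Kaplan-Meier analysis needs one start, one list of events and one list of censoring points. Here the end of response is relapse in one section and progressive disease, death or study end in two others. Study end can only be censoring, so that list mixes the two kinds without labels. Two analysts following different sections could code the same patient differently, and this reaches the main DOR analysis.

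The sensitivity analysis has a separate weakness. Whether a responder is included depends on a transplant that comes after the DOR clock starts. A responder transplanted in remission loses all observed remission time, while one who relapses before a planned transplant stays in. The result then reflects the timing of relapse relative to transplant as well as how long responses last.

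**Working it through.** **1. One patient under each section**

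| Course after response | 11.1.5 | 13.3.2.3 and 13.7 |
|---|---|---|
| Dies in remission | No event | Listed end point; event or censoring not stated |
| Marrow blasts rise from 2% to 3% at unchanged cellularity | No relapse, since not above 5% | Read literally, progressive disease: (3 − 2)/2 = 50%, above the 25% threshold |
| CRi, then blasts above 5% | Clock started, but relapse is defined only after CR | Progressive disease if the rise is at least 25% |

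The second row shows that a relative rise in blasts is a poor end-of-response criterion for someone in remission.

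**2. How much the status of death could matter**

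The plan states no DOR figure, so there is none to reproduce. As a scale only, take the 5.9-month median relapse-free survival in 2.2.1.2.2 and assume exponential times. If a share *d* of responses end in death without relapse (assumed, constant hazard), the median with death as an event is 5.9 × (1 − *d*):
- *d* = 10%: 5.3 months
- *d* = 20%: 4.7 months

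With death censored, the median is 5.9.

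**3. The exclusion**

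Assumptions, none from the plan: a share *s* of responders is scheduled for transplant at a time *H* uniform over 1 to 4 months after response; scheduling is unrelated to prognosis; nobody is transplanted after relapse. The response time *T* is exponential.

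- Rate: λ = ln 2 / 5.9 = 0.1175 per month.
- Chance that a scheduled patient relapses first: P(T < H) = 1 − (e^(−λ) − e^(−4λ))/(3λ) = 1 − 0.749 = 0.251.
- Share of all responders remaining after exclusion: (1 − s) + 0.251s.
- For a median *m* of at least 4 months, solve [(1 − s)(1 − e^(−λm)) + 0.251s] / [(1 − s) + 0.251s] = 0.5.

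At s = 40%, the denominator is 0.600 + 0.100 = 0.700 and half of it is 0.350. Then 1 − e^(−λm) = (0.350 − 0.100)/0.600 = 0.416, so m = 4.6 months. For s = 60% the median falls below 4 months, so 0.251 in the numerator is replaced by P(T ≤ m, T < H).

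| Scheduled | Transplanted in remission | Median with exclusion | Shift from 5.9 |
|---|---|---|---|
| 10% | 7.5% | 5.7 | −0.2 |
| 20% | 15.0% | 5.4 | −0.5 |
| 40% | 30.0% | 4.6 | −1.3 |
| 60% | 45.0% | 3.3 | −2.6 |

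Censoring at transplant returns 5.9 in every row, because referral is assumed unrelated to prognosis.

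**4. If transplant after relapse is also excluded**

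Completed DORs are then dropped as well, which pushes the other way. At 40% scheduled, with 25, 50 or 100% of those who relapse first still transplanted, exclusion gives 4.9, 5.2 and 5.9 months.

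**5. Sampling noise**

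Section 13.5 anticipates a CR rate of about 40%; 0.40 × 12 = 4.8, or about 5 responders. With fully observed exponential times and a true median of 5.9, the central 95% range of the sample median is about 1.4 to 16 months with 5 responders, and about 2.5 to 12 months even if all 12 respond.

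**6. Limit of the remedy**

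If referral depends on prognosis, censoring is biased too. With two equal prognostic groups, a hazard ratio of 2 and 40% scheduled overall (60% against 20%), censoring gives 5.6 months when good-prognosis patients are favoured and 6.3 when poor-prognosis patients are. At hazard ratio 3 (70% against 10%), poor-prognosis referral and no transplant after relapse, censoring gives 6.9 and exclusion 5.4, so exclusion is then closer to 5.9.

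**The case against.** **Death.** A reader might infer that a death in remission is an event in Section 13 and not in 11.1.5. The text does not establish that. Sections 13.3.2.3 and 13.7 never label death, and if it is a censoring point the Kaplan-Meier estimate treats it as a relapse-only definition would. This objection stands: the supportable statement is that the status of death is unspecified. The mismatch between relapse and progressive disease, and the CRi gap, remain on either reading.

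**Timing of transplant.** A reader might also take 13.7 to exclude transplants both before and after relapse. That is an inference from open wording combined with the follow-up rule in 5.8. Section 5.3.1 links transplant to a documented response and 2.3.3 speaks of consolidation, so transplant in remission is the natural reading. Even so, the analysis still selects on a later event.

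**Share affected.** It is tempting to say that most responders would be removed. Section 5.7 says many patients will be candidates, but 2.3.3 says only a subset of those in remission will be, and candidates are not all transplanted. At 10 to 20% scheduled, the modelled shift is only 0.2 to 0.5 month.

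**Importance.** The sensitivity analysis is optional and supplements an all-responder Kaplan-Meier estimate that the exclusion does not touch. DOR among responders who were not transplanted is a readable description, and censoring is not guaranteed to be less biased. This stands, and is why the transplant point is secondary.

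**Conclusion.** The definition conflict holds on the face of the text. DOR has different end points in 11.1.5 and in 13.3.2.3/13.7, its events and censoring points are unlabelled, and the relapse definition leaves CRi responders uncovered. This affects how individual responders are coded in the main analysis.

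The transplant exclusion is a lesser fault of the same endpoint. It conditions on the future and discards observed remission time. In the simplest scenario it lowers a 5.9-month median to between 5.7 and 3.3 months as the scheduled share goes from 10 to 60%. Those figures rest on an assumed exponential model, transplant window and referral pattern; the only related timing rule is the interval off nivolumab before transplant in 5.6. A reader might infer that the exclusion must shorten DOR, but the documents do not fix the net direction, since referral pattern and any exclusion after relapse can offset or reverse it.

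Severity is minor. The endpoint is secondary and descriptive, the modelled shifts are smaller than sampling noise with 5 to 12 responders, and no dose or stopping decision depends on DOR.

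**What to change.** **Definition.** Use one rule in 11.1.5, 13.3.2.3 and 13.7. DOR runs from the first record of CR or CRi. Relapse as in 11.1.2, extended to cover relapse after CRi, or death from any cause, is an event. Patients event-free at last disease assessment or study end are censored. Drop progressive disease as the end of a response.

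**Sensitivity analysis.** Keep the all-responder Kaplan-Meier analysis as the main one. Replace the exclusion with: responders who undergo allogeneic transplant while still in response are censored at the transplant date, and a relapse before transplant remains an event. State that this censoring may be informative, because referral is discretionary, and that the result is to be read beside the main analysis.

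**Cost.** A few sentences. Relapse, survival and subsequent-treatment data are already collected (5.7, 5.8, Study Calendar footnote 17), and the 100-day post-transplant monitoring already needs the transplant date. The gain is a clearly stated quantity that keeps every responder's observed time up to transplant, without a promise of lower bias.
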